7.4.1 Pregnancy

At the time a Principal Investigator or site personnel becomes aware that a study participant became pregnant following study participation, the Principal Investigator or designee will report the pregnancy immediately by phone and/or by faxing a completed Pregnancy Report to [REDACTED] within one working day of being notified of the pregnancy report.

The report will include the following elements:

- Participant (mother's) coded study identifier;
- Date of participant's last menstrual period;
- Total accumulated dose of study treatment administered to date;
- Date of study medication administration.

The investigator will follow the subject until completion of the pregnancy and must assess the outcome in the shortest possible time but not more than 30 days within completion of the pregnancy.

Upon delivery, miscarriage or abortion, the Principal Investigator or designee must forward a follow-up Pregnancy Report with any relevant information on the present condition of the fetus to the Symbio, including:

- Mother's coded study identifier(s);
- Gestational age at delivery, miscarriage or abortion;
- Birth weight, gender, length and head circumference, if available;
- Apgar scores recorded after birth, if available;
- Any abnormalities.

If the outcome of the pregnancy **meets the criteria for immediate classification of an SAE** (e.g., spontaneous or therapeutic abortion [any congenital anomaly detected in an aborted fetus is to be documented], stillbirth, neonatal death, or congenital anomaly), the investigator will report the event by phone and by faxing a completed SAE report form to [REDACTED] within one working day of being notified of the pregnancy report.

Protocol No: PRG-NY-16-009

If the trial is completed before the outcome of the pregnancy is known, [REDACTED] will assume the responsibility for following up on the pregnancy. [REDACTED] will contact the Investigator or Study coordinator on or around the potential expected date of delivery to follow-up on the outcome of pregnancy and will also check on the status of the infant 8 weeks post-delivery. Upon awareness of the pregnancy outcome and known status of the infant following 8 weeks of delivery, the investigator will complete the applicable pregnancy report forms and fax to [REDACTED] within 1 day of being notified.

7.5 Post Study Adverse Events

7.5.1 Non-serious Adverse Events

Adverse events that are identified at the last assessment visit (or the early termination visit) must be recorded on the AE CRF with the status of the AE noted.

7.5.2 Serious Adverse Events

Serious adverse events that are identified on the last assessment visit (or the early termination visit) must be recorded on the AE CRF page and reported to Perrigo according to the procedures outlined above. Subjects with unresolved previously reported serious adverse events, or any new serious adverse events identified on the last assessment visit, should be followed by the investigator until the events are resolved, or the subject is lost to follow-up. Resolution means the subject has returned to the baseline state of health, or the investigator does not expect any further improvement or worsening of the adverse event. The investigator should continue to report any significant follow-up information to Perrigo up to the point that the event has resolved. Any serious adverse event reported by the subject to the investigator that occurs after the last assessment, and are determined by the investigator to be reasonably associated with the use of the study drug, should be reported to Perrigo.

8. STATISTICAL ANALYSIS

The sections that follow highlight sample size determination and the planned analyses for this study. A statistical analysis plan (SAP) will be prepared separately from this protocol which gives descriptions of the statistical methods, models, hypotheses and subject populations to be analyzed. The SAP will be completed and approved before locking the database and unblinding the study and will serve as a companion to the protocol and the *de facto* documentation of the proposed statistical evaluation. The SAP will be completed and finalized prior to breaking the blind.

8.1 Statistical Analysis Plan

8.1.1 Analysis Populations

The following populations are defined for the purpose of analyses:

- Intent-to-Treat (ITT) (safety population): Any subject that was randomized, received and used study medication.

Protocol No: PRG-NY-16-009

- Modified Intent-to-Treat (mITT): Any subject, who met the inclusion/exclusion criteria, was randomized, received and used the study medication, and returned for at least one post-baseline efficacy assessment.
- Per Protocol (PP): Any subject:
 - Who met inclusion/exclusion criteria,
 - Who was randomized and received and used study medication,
 - Who met the protocol criteria for compliance [REDACTED]
and
 - Who completed Visit 4/Week 12/Day 84 (End of Treatment/Early Termination Visit) within window OR was discontinued from the study due to treatment failure.
 - Without significant protocol violations that could have interfered with the administration of the treatment or the precise evaluation of treatment efficacy.

[REDACTED]
[REDACTED]
[REDACTED]
[REDACTED]

8.1.2 Planned Analysis

All randomized subjects who received/used study medication will be evaluated for safety. The efficacy analysis will be conducted on both the PP and the mITT subject populations. Two-sided hypothesis testing will be conducted. Resulting p-values less than 0.05 will be considered statistically significant. No adjustments of p-values for multiple comparisons will be made. No interim analyses are planned. SAS software will be used for all data analyses and tabulations.

The treatment response will be summarized by treatment group for the end-of-treatment evaluation.

The primary efficacy endpoint will be the mean percent change from baseline to Visit 4/Week 12 (Day 84) in the inflammatory (papules and pustules) lesion count.

The secondary endpoint will be the proportion of subjects with clinical success defined as a score of clear or almost clear (score of 0 or 1) on the Investigator Global Assessment (IGA) at Visit 4/Week 12 (Day 84).

[REDACTED]
[REDACTED]

8.1.3 Sample Size Considerations

8.1.4 Efficacy Measures and Analysis

Clinical endpoints

The primary efficacy measure will be the mean percent change from baseline to Visit 4/Week 12 (Day 84) in the inflammatory (papules and pustules) lesion counts. The secondary efficacy measure will be the proportion of subjects with clinical success defined as a score of clear or almost clear (score of 0 or 1) on the Investigator Global Assessment (IGA) at Visit 4/Week 12 (Day 84).

Equivalent efficacy

For the mean percent change from baseline in the inflammatory lesion count, the Test treatment will be considered to be therapeutically equivalent to the Reference treatment if the 90% confidence interval on the Test-to-Reference ratio of means, calculated by Fieller's Method, falls within the interval 0.80 to 1.25. The treatment means and estimate of residual variance for the confidence interval calculation will come from an Analysis of Variance of the Test and Reference results using a statistical model containing terms for Treatment and Site.

For the proportion of subjects with clinical success, the Test treatment will be considered to be therapeutically equivalent to the Reference treatment if the 90% confidence interval on the difference between Test and the Reference proportions is contained within the interval -20% to +20%. The confidence interval will be constructed using Wald's method with Yates' continuity correction.

Therapeutic equivalence evaluations in the per-protocol (PP) population will be considered definitive and those in the mITT will be considered supportive.

Superiority

For the mean percent change from baseline in the inflammatory lesion count, each active treatment will be evaluated to determine if it has superior efficacy to that of the Vehicle at Visit 4/Week 12 (Day 84) via an Analysis of Variance using Proc Mixed of SAS with Treatment and Site as factors.

The proportion of subjects with clinical success for each active treatment will be compared to that of the Vehicle using Z-test with Yate's continuity correction.

Superiority tests will be two-sided at a significance level of $\alpha = 0.05$. Superiority analyses in the mITT population will be considered definitive and those in the PP will be considered supportive

8.1.5 Safety and Adverse Events Analysis

The frequency and percent of subjects with adverse events will be summarized by MedDRA system organ class and preferred term and by severity and relationship to study drug for all three treatment groups.

The comparable safety of the Test and Reference treatments will be evaluated by statistical comparison of the proportion of subjects who reported any adverse events. Safety comparisons will be performed only for the safety intent-to-treat population.

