2.2 Safety

Safety of the test and reference products will be compared by evaluating the nature, severity and frequency of their adverse event profiles. All adverse events that occur during the study will be

recorded. Descriptions of reactions or complaints will include the approximate date of onset, the date the adverse event ended, the severity of the adverse event, and the outcome. Comparisons between the treatment groups will be made by tabulating the frequency of subjects with one or more adverse events (classified into MedDRA terms) during the study. Pearson's Chi-Square test or Fisher's Exact test, whichever is most appropriate, will be used to compare the proportion of subjects in each treatment group with any adverse event. The adverse events reported by at least five percent of the subjects in any treatment group will be summarized descriptively.

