5.1 Methodological Considerations

The study will be conducted under the same protocol across all the sites. No formal statistical analyses are planned to evaluate the consistency of efficacy results across the multiple clinical sites. These results, however, will be tabulated and if a site's efficacy data are obviously inconsistent with the results across all sites, this will be explored and addressed in the final study report.

All randomized subjects who received study medication will be evaluated for safety using ITT population. The efficacy analysis will be conducted on both the PP and the mITT populations.

Two-sided hypothesis testing will be conducted for all the tests. Resulting p-values less than 0.05 will be considered statistically significant unless noted otherwise. No adjustments of p-values for multiple comparisons will be made. No interim analyses are planned.

SAS software will be used for all data analyses and tabulations.

5.2 [REDACTED]

[REDACTED]

[REDACTED]

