5.6 Safety Variables and Analyses

Duration of Treatment and Medication Compliance

Number of applications, days of exposure, and compliance rate will be summarized by treatment group using descriptive statistics. For each subject, the overall duration of treatment (days) will be calculated using the following formula:

$$(\text{Date of last application of study medication}) - (\text{Date of first application of study medication}) + 1.$$

Medication compliance rate (%) will be calculated for each subject as follows:

$$(\text{Total number of applications used}) / (\text{Expected number of applications}) * 100\%.$$

[REDACTED]

Adverse Events

Adverse events (AEs) will be coded in MedDRA, version 18.1. Treatment-Emergent Adverse Event (TEAE) is defined as any AE occurs on or after application of the first dose of study drug. Number and percent of subjects reporting TEAEs will be tabulated by treatment group. Summaries will be presented by body system and preferred term for the ITT population, and

further by severity and relationship to study medication. TEAEs reported by 5% or more subjects for any treatment group will also be summarized. In the summaries of incidence rates (frequencies and percentages), severity and relationship to study drug, subjects who report more than one event that are mapped to the same preferred term will be counted only once under the strongest severity and relationship, accordingly. The difference between Test and Reference treatments with regard to the severity and frequency of their dermatological adverse events will be statistically evaluated. Chi-Square or Fisher's exact test will be used to compare the proportions of subjects of the two active treatment groups who report any TEAE.

Treatment-Emergent Serious Adverse Events (TESAEs) will be discussed within the clinical study report. TEAEs, TESAEs and TEAEs that led to treatment interruption or discontinuation will be presented in data listings.

Concomitant Medications, Laboratory Values, and Vitals Signs

Concomitant medications will be coded using the WHO Drug Dictionary, version September 2015, and will be presented in data listings. All vital signs data will be displayed in listings.

Erythema Severity and Application Site Reaction Assessments

Frequency and distribution of erythema severity assessment and application site reactions of dryness, scaling/peeling, pruritus, burning/stinging, pain and will be summarized and compared descriptively by visit.

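### Comparable safety of Test and Reference rests on a difference test with no confidence interval or margin, so a non-significant p-value would not show comparability

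*Protocol*

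**What the plan says.** Comparing the safety of Test and Reference is part of the study objective in both documents. Protocol 8.1.5 sets out how: "The comparable safety of the Test and Reference treatments will be evaluated by statistical comparison of the proportion of subjects" with any adverse event. That section names no test. Two other places do:

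- Protocol 2.2: "Pearson's Chi-Square test or Fisher's Exact test, whichever is most appropriate, will be used to compare the proportion of subjects" with any adverse event in each treatment group.
- SAP 5.6: "Chi-Square or Fisher's exact test will be used to compare the proportions of subjects of the two active treatment groups who report any TEAE".

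The general rules apply to these tests. SAP 5.1 says "Two-sided hypothesis testing will be conducted for all the tests", and Protocol 8.1.2 says "Resulting p-values less than 0.05 will be considered statistically significant".

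The plan also has other safety material. Protocol 2.2 compares the nature, severity and frequency of the adverse event profiles. Protocol 8.1.5 and SAP 5.6 tabulate events by MedDRA term, severity and relationship, and events reported by at least 5% of any group are summarised. Application-site scores are compared descriptively by visit. SAP 5.6 adds that the Test–Reference difference in the "severity and frequency of their dermatological adverse events will be" statistically evaluated, without naming a method.

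**The concern.** A chi-square or Fisher test starts from the hypothesis that the two rates are equal and looks for evidence against it. Failing to find that evidence is not evidence of equality. The less information a trial holds, the more readily it returns a non-significant result, so a small or noisy trial would look more comparable than a large one.

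The plan uses the appropriate logic for efficacy. There the null is non-equivalence, and a 90% interval must lie within stated limits: 0.80 to 1.25 for the lesion-count ratio and −20% to +20% for clinical success (Protocol 8.1.4; SAP 5.5.1 and 5.5.2). Safety belongs to the same Test-versus-Reference objective, yet its one named inferential method works the other way and yields no estimate of the difference. At stake is the wording of the safety conclusion: a real excess of adverse events on the generic could be reported only as not significantly different.

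**Working it through.** There is no figure in the plan to reproduce. The sample size and allocation ratio are redacted, and no power, margin or expected any-event rate for safety is visible.

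**Inputs**

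- Two-sided α = 0.05 (Protocol 8.1.2; SAP 5.1).
- Application-site pain 6.2% (Protocol 7). This is one reaction, not the any-event rate.
- Assumed: any-event rate of 10% or 20% in the Reference arm.
- Assumed: 100, 200, 300 or 400 per active arm, 1:1.

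**Step 1. Chance that a true doubling (p to 2p) gives p ≥ 0.05.** With n per arm and p̄ the mean of the two rates:

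- SE0 = √[2·p̄(1−p̄)/n]
- SE1 = √[(p1(1−p1) + p2(1−p2))/n]
- power = Φ[(|p2−p1| − 1.96·SE0)/SE1], and the miss rate is 1 − power.

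Example, 6.2% to 12.4% with n = 200: p̄ = 0.093, SE0 = √(2×0.093×0.907/200) = 0.02904, and SE1 = √[(0.062×0.938 + 0.124×0.876)/200] = 0.02888. Then (0.062 − 1.96×0.02904)/0.02888 = 0.176, power = 0.570 and the miss rate is 43.0%.

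| True rates | 100 | 200 | 300 | 400 |
|---|---|---|---|---|
| 6.2% to 12.4% | 67.5% | 43.0% | 25.5% | 14.3% |
| 10% to 20% | 49.2% | 19.8% | 6.9% | 2.2% |
| 20% to 40% | 12.4% | 0.7% | <0.1% | <0.1% |

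Enumerating the binomial outcomes gives close agreement for the Pearson test. Fisher's test misses more: 75%, 49%, 29% and 16% in the first row.

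**Step 2. What the p-value leaves out.** Suppose 10/200 on Reference and 20/200 on Test report an event. Pearson gives p = 0.058 and Fisher p = 0.086, so neither is significant. The risk difference is 5.0 points, with SE = √[(0.05×0.95 + 0.10×0.90)/200] = 0.0262. The simple Wald 95% interval is 5.0 ± 1.96×2.62, or −0.1 to 10.1 points. The interval shows that an excess of about 10 points is not excluded; the p-value does not.

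**Step 3. Dependence on the choice of test.** With 12/200 against 24/200, Pearson gives p = 0.036 and Fisher p = 0.053. The risk difference is 6.0 points (Wald 95% interval 0.4 to 11.6) whichever test is used.

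**Step 4. Precision an interval would give.** At equal true rates the half-width is 1.96·√[2p(1−p)/n]. At 10% it is 8.3, 5.9, 4.8 and 4.2 points for 100 to 400 per arm. At 20% it is 11.1, 7.8, 6.4 and 5.5 points.

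**The case against.** Three stronger readings are tempting, and the documents support none of them.

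- **That the plan declares the products comparable when p ≥ 0.05.** No such rule is written. Explicit decision rules of that kind appear only for efficacy, and Protocol 2.2 also relies on the nature, severity and frequency of events. The risk lies in how a result would be read.
- **That a doubled adverse-event rate would be missed.** The tested endpoint is any adverse event, whose rate is not given. The 6.2% figure belongs to one reaction, and arm sizes are redacted. If the any-event rate is 20% and there are 200 or more per arm, a doubling would almost always be detected.
- **That pooling all events hides application-site reactions.** SAP 5.6 evaluates dermatological events separately, and the tables by term, the 5% summary and the visit-by-visit application-site scores would show an imbalance as counts. What is missing is only the method and event grouping for the dermatological evaluation.

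A further objection is that an interval without a margin does not prove comparability either, and a reader may simply check whether it includes zero. That is correct as far as it goes. The interval still states which excess remains possible, and the p-value does not.

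None of this makes a non-significant difference test evidence of comparability, and the descriptive tables do not provide an inferential statement.

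**Conclusion.** The point holds as a gap between the stated purpose and the only named inferential method. A two-sided 0.05 difference test, with no interval or margin, cannot support a conclusion of comparable safety.

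The size is conditional on the assumed arm sizes, 1:1 allocation and background rates. The undetected share of true doublings is substantial for a single reaction near 6%, moderate to small for an any-event rate of 10% once arms reach 200, and negligible for 20% at that size. The documents do not show which case applies.

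The efficacy decisions are unaffected. This is a cheap and worthwhile improvement to how the safety comparison is estimated and worded.

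**What to change.** In Protocol 2.2 and 8.1.5 and in SAP 5.6:

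1. Report the Test-minus-Reference risk difference with a two-sided 95% score-based confidence interval for any TEAE, and separately for dermatological/application-site TEAEs. Define that event group, so that the SAP's dermatological evaluation has a named method.
2. Word the safety conclusion by the largest excess on Test that the interval does not exclude.
3. Keep the chi-square or Fisher p-value as descriptive, and state that p ≥ 0.05 is not evidence of comparability.

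This uses data already collected and needs no extra subjects or change in conduct. The cost is a little more analysis and wording, and a less strongly worded safety conclusion when the interval is wide.

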8.2 Comparability of Subjects at Baseline

Descriptive statistics will be presented, by treatment group, for subject baseline characteristics. The significance of any obvious treatment group differences will be discussed in the CSR.

9. CONSENT CONSIDERATIONS AND PROCEDURES

It will be made clear to the subject that, for the purposes of the study, they are consenting only for topical application of medication or vehicle. Investigators may discuss the availability of the study and the possibility for entry with a potential subject without first obtaining consent. However, informed consent must be obtained and documented prior to initiation of any procedures that are performed solely for the purpose of determining eligibility for research, including withdrawal from current medication(s). When this is done in anticipation of, or in preparation for, the research, it is considered to be part of the research.

The study must be approved in writing by an appropriate IRB as defined by FDA regulations. A copy of the Letter of Approval from the IRB, which also contains specific identification of the documents approved, must be received by Perrigo, prior to study commencement.

Periodic status reports must be submitted to the IRB at least annually as required by the site's IRB, as well as notification of completion of the study and a final report within three months of study completion or termination. A copy of all reports submitted to the IRB must be sent to Perrigo.

The investigator(s) has both ethical and legal responsibility to ensure that each subject being considered for inclusion in this study is given a full explanation of the protocol. This shall be

Protocol No: PRG-NY-16-009

documented on a written informed consent form, which shall be approved by the same Institutional Review Board (IRB) responsible for approval of this protocol. Each informed consent form shall include the elements required by FDA regulations in 21 CFR Part 50. The investigator agrees to obtain approval from Perrigo of any written informed consent form used in the study, preferably prior to submission to the IRB.

Once the appropriate essential information has been provided to the subject and fully explained by the investigators (or a qualified designee) and it is felt that the subject understands the implications of participating, the IRB-approved written informed consent form shall be signed by the subject (or their parent/legally authorized representative) and the person obtaining consent (investigator or designee). The subject shall be given a copy of the signed informed consent form and the investigator shall keep the original on file.

If the subject fails to meet the inclusion/exclusion criteria at the conclusion of the screening phase, the subject will be withdrawn from screening. In the event that the subject is re-screened for study participation, a new informed consent form must be signed.

